### **8.19.1 Monitoring of Laboratory Abnormalities**

All laboratory values will be assessed by the Investigator to determine clinical significance. All abnormal laboratory values considered clinically significant by the Investigator will be recorded in the adverse event page of the eCRF. Abnormal laboratory values may be considered clinically significant if they are accompanied by signs/symptoms and/or require medical intervention. Abnormal laboratory values occurring during the clinical study are to be followed until repeat test results return to normal (or baseline), stabilize, or the subject is lost to follow-up.

### **8.20 Urine Drug Screen**

A urine drug screen will be performed at Screening (Visit 1) and at Visit 2. The analytes will include opiates, cocaine, amphetamines, and barbiturates.

### **8.21 Blood Pharmacokinetic (PK) Evaluations**

At Visit 2 a pre-dose trough sample will be drawn immediately prior to the AM dose. The subject will take their first dose at the site with the dose time and date recorded in the eCRF. A PK blood draw will be collected within the first 4 hours after the dose (at any time between 30 minutes to 4 hours post-dose).

At Visit 3, Visit 7, Visit 9, and Visit 10 (or Early Termination), subjects will return to the clinic prior to taking their AM dose. A pre-dose trough sample will be drawn at Visit 3 and Visit 7 immediately prior to the AM dose. The subjects will then take their dose of study drug on-site and the exact time of the dose ingestion will be recorded. A single post-dose sample will be drawn from each subject while on-site at the clinic at 60 minutes  $\pm$  30 minutes, and at 2 hours  $\pm$  30 minutes, respectively.

At Visit 9 and Visit 10 single post dose sample will be drawn from each subject while on-site at the clinic at 3 hours  $\pm$  30 min and at 4 hours  $\pm$  30 min, respectively. The exact time of the last dose of study drug will be recorded.

In all cases, the exact clock time of each PK sample will be recorded.

Plasma samples will be quantified for COR388 (and potential metabolites of interest). Data will be analyzed by a population pharmacokinetic approach to derive COR388 (and potential metabolites of interest) systemic exposure metrics. A

detailed population PK analysis plan will be generated and finalized prior to the PK analysis being initiated.

## 8.22 Cerebrospinal Fluid (CSF) Evaluations

The LP procedures, and medical care of the subject, will be administered as per clinical site standards including imaging prior to procedure, if applicable. Cerebrospinal fluid will be tested for measurement of bacterial DNA (*Pg*) using qPCR, biomarkers of AD, and gingipain activity. The details of sample collection and processing procedures will be provided in the Laboratory Manual. CSF samples will be sent to the central laboratory to be distributed to a specialty laboratory for biomarker analysis.

Assessments will be performed up to 7 days prior to study drug dosing at Baseline (Visit 2) and Visit 10 (or Early Termination).

## 8.23 Electrocardiograms (ECGs)

Standard 12-lead electrocardiograms (ECGs) will be performed at Screening (Visit 1), Visit 2, Visit 3, Visit 4, Visit 5, Visit 7, Visit 9, Visit 10 (or Early Termination), and Visit 11 (Safety Follow-up Visit). The Investigator will review ECGs for any changes from baseline. At Visit 2, Visit 3, Visit 7, Visit 9, and Visit 10 (or Early Termination), subjects will take their dose on-site and the exact time of the dose ingestion will be recorded. The time to maximum plasma concentration of COR388 ( $T_{max}$ ) is approximately 1-1.5 hours. At visits when the subject takes their dose of study drug on-site, ECGs should be measured approximately 1-1.5 hours after dosing. At Visit 3 and Visit 7, ECGs will also be performed at trough (prior to dosing). ECGs will be reviewed by a cardiologist at the central ECG laboratory to identify any abnormalities and verify automatically calculated values of RR, PR, QRS, and QTc intervals. Clinically significant ECG events and abnormalities will be recorded as adverse events.

Open Label Extension: Standard 12-lead ECGs will be performed at Visits OLE-1, OLE-2, OLE-4, OLE-6 (or Early Termination) and OLE-9 (OLE Safety Follow-Up Visit). **NOTE:** Effective 16 February 2021, the OLE portion of the study was terminated by the Sponsor.

## 8.24 Safety Monitoring Plan for Potential Drug Induced Liver Injury

This study is being conducted in compliance with FDA Guidance for Industry on Drug-Induced Liver Injury (DILI), which can be accessed at: <https://www.fda.gov/media/116737/download>.

If a study patient experiences any signs or symptoms of hepatic illness including loss of appetite, nausea, vomiting, fever, weakness, tiredness, right upper quadrant tenderness, itching, yellowing of the skin and eyes, light colored bowel movements or dark colored urine, or AST or ALT elevation at any time during subject's

participation in COR388-010 study, the following safety measures will be implemented:

1. Verify previous liver enzymes (ALT, AST) as well as any other liver-related lab parameters (e.g., INR, alkaline phosphatase, bilirubin (total, direct, indirect), etc.)
2. Perform detailed review of medical history, especially prior evidence of viral hepatitis, cholestasis and other associated conditions and ensure complete and accurate data entry in EDC.
3. Perform detailed review of concomitant medications including OTC or herbal products and ensure complete and accurate data entry in EDC.
4. Contact the Study Medical Monitor and report on the clinical subject status.
5. Arrange a confirmatory testing within 48-72 hours and repeat until the abnormality is stabilized or resolved.
6. Between V4/Week 6 – V8/Week 32 and OLE-2/Week 54 – OLE-5/Week 84 subject must have LFT testing performed at each per protocol required visit. If such testing is not performed at any of the visits, the IP administration must be halted until the testing is done.
7. If a patient reports any gastrointestinal symptoms at any time during the study, safety laboratory testing must be performed promptly (stat labs).

**If AST or ALT is >2x ULN – perform weekly testing until the abnormality resolves.**

**If AST or ALT is >3x ULN, please continue as follows:**

1. Ensure repeat testing (ALT, AST, ALP, GGT, bilirubin, eosinophils (differential count) 2-3 times weekly until baseline levels are re-established or another frequency is agreed upon with the medical monitor.
2. Rule out acute viral hepatitis (A, B, C, D, and E) and arrange for an abdominal ultrasound/MRI/CT.
3. Obtain additional tests to evaluate liver function, as appropriate (e.g., INR, direct bilirubin, auto-antibodies, bile salts/acids).
4. Tests for infection with cytomegalovirus, Epstein-Barr virus, and herpes simplex virus, if fever, rash or lymphadenopathy occur.
5. Serum anti-nuclear antibody, anti-smooth muscle antibody, and IgG concentrations.
6. Consider gastroenterology or hepatology consultations.
7. Please ask the patient to:
  - *Give detailed history of any symptoms and prior or concurrent diseases (please ask with same frequency as repeated blood tests are performed).*
  - *Confirm concomitant drug use (incl. non-prescription drugs, herbal supplements, etc.)*
  - *Provide information about any alcohol use*

- *Provide information about any exposure to environmental chemical agents.*

**Treatment should be stopped if:**

- ALT or AST >8xULN
- ALT or AST >5xULN for more than 2 weeks
- ALT or AST >3xULN and (TBL >2xULN or INR >1.5)
- ALT or AST >3xULN with the appearance of worsening of fatigue, nausea, vomiting, right upper quadrant pain or tenderness, fever, rash, or eosinophilia

**Rechallenge should not be attempted if:**

- ALT or AST >5xULN
- ALT or AST >3xULN and (TBL >2xULN or INR >1.5)
- ALT or AST >3xULN with the appearance of worsening of fatigue, nausea, vomiting, right upper quadrant pain or tenderness, fever, rash, or eosinophilia

## **9 ADVERSE EVENT REPORTING**

Throughout the course of the study, all adverse events (AEs) will be monitored and recorded on an AE eCRF, including the AE's description, start and end date, seriousness, severity, action taken, and relationship to the investigational product. If AEs occur, the first concern will be the safety of the study subjects. All AEs will be followed until resolved or stable and the outcome documented on the eCRF.

Open Label Extension: Adverse events will be monitored at all visits and phone calls. **NOTE:** Effective 16 February 2021, the OLE portion of the study was terminated by the Sponsor.

### **9.1 Definitions and Criteria**

#### **9.1.1 Adverse Events**

Per ICH E2A: An AE is any untoward medical occurrence in a subject or clinical investigation subject administered a pharmaceutical product and which does not necessarily have to have a causal relationship with this treatment. An AE can therefore be any unfavorable and unintended sign (including an abnormal laboratory finding, for example), symptom, or disease temporally associated with the use of a medicinal product, whether or not considered related to the medicinal product.

Medical interventions such as surgeries, diagnostic procedures, and therapeutic procedures are not AEs but the action taken to treat the medical condition. They should be recorded as treatment of the AEs.

### **9.1.2 Serious Adverse Events**

A serious adverse event (SAE) or reaction is any untoward medical occurrence that at any dose:

- Results in death
- Is life-threatening
- Requires inpatient hospitalization or prolongation of existing hospitalization
- Results in persistent or significant disability or incapacity
- Is a congenital anomaly or birth defect
- Is an important medical event (e.g., intensive treatment in an emergency room or at home for allergic bronchospasm; blood dyscrasias, or convulsions that do not result in hospitalization; or development of drug dependency or drug abuse; malignancy tumors [histologically different from primary tumor])

Note: The term “life-threatening” in the definition of “serious” refers to an event in which the subject was at risk of death at the time of the event; it does not refer to an event that hypothetically might have caused death if it were more severe.

In this study, hospitalization is defined to be at least 24-hours in duration.

Medical and scientific judgement should be exercised in deciding whether expedited reporting is appropriate in other situations, such as important medical events that may not be immediately life-threatening or result in death or hospitalization but may jeopardize the subject or may require intervention to prevent one of the other outcomes listed in the definition above. These should also usually be considered serious.

Examples of such events are intensive treatment in an emergency room or at home for allergic bronchospasm; blood dyscrasias, or convulsions that do not result in hospitalization; or development of drug dependency or drug abuse.

The term “severe” is often used to describe the intensity (severity) of a specific event (as in mild, moderate, or severe); the event itself, however, may be of relatively minor medical significance (such as a severe headache). This is not the same as “serious,” which is based on the outcome or action associated with events, as described above. Seriousness (not severity) serves as a guide for defining regulatory reporting obligations.

### **9.1.3 Unexpected Adverse Drug Reactions**

An unexpected adverse drug reaction (ADR) is a reaction for which the nature or severity is not consistent with the applicable product information (IB, Package Insert for marketed products). Until product information is amended, expedited reporting is required for additional occurrences of the reaction. Reports that add significant

information on specificity or severity of a known, already documented SAE constitute unexpected events. For example, an event more specific or more severe than described in the IB would be considered "unexpected." Specific examples would be (a) acute renal failure as a labeled ADR with a subsequent new report of interstitial nephritis and (b) hepatitis with a first report of fulminant hepatitis.

Guidance on reporting AEs and SAEs is described in [Section 9.2](#).

#### **9.1.4 Abnormal Laboratory Values**

Any abnormality in a laboratory value that is new in onset or which has worsened in severity or frequency from the baseline condition and meets 1 of the following criteria will be recorded on the AE pages of the eCRF:

- Requires therapeutic intervention or diagnostic tests;
- Leads to discontinuation of investigational product;
- Has accompanying or inducing symptoms or signs; and/or
- Is judged by the Investigator as clinically significant.

#### **9.1.5 Assessing Intensity and Relationship**

All AEs will be assessed on 2 descriptive parameters: intensity and relationship to the investigational product:

- Intensity refers to the severity of an event and references impact on a subject's functioning.
- Relationship refers to the likelihood that the event being assessed was caused by the investigational product.

#### **Intensity**

Each AE will be classified according to the following criteria:

- |           |   |
|-----------|---|
| Mild:     | The AE does not interfere in a significant manner with the subject's normal level of functioning.                         |
| Moderate: | The AE produces some impairment of functioning but is not hazardous to the subject's health.                              |
| Severe:   | The AE produces significant impairment of functioning or incapacitation and is a definite hazard to the subject's health. |

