### **11.3.3 Safety Analysis**

#### **11.3.3.1 Adverse Events**

Adverse events will be coded by Preferred Term (PT) using the Medical Dictionary for Regulatory Activities (MedDRA) classification.

A treatment-emergent adverse event (TEAE) is defined as any AE that has an onset on or after the first dose of study drug, or any pre-existing condition that has worsened on or after the first dose of study drug. The incidence of TEAEs, treatment-related TEAEs, SAEs including deaths, TEAEs that lead to discontinuation of investigational product, and TEAEs by maximum severity and relationship to study drug will be summarized by MedDRA system organ class, PT, and treatment group.

To assess the potential for abuse associated with the administration of COR388 HCl, a systematic review of TEAE terms suggestive of the potential for abuse will be conducted for all clinical studies in subjects who received at least 1 dose of COR388 HCl and a summary of this information will be included in the regulatory submission. As a general framework for data collection and analysis we will use the overall abuse flag terms in the FDA Guidance (2017).

Since the target patient population are elderly, have substantial comorbidity and are often on other medications, a careful assessment and documentation of adverse event causality will be made in order to ensure that false positive TEAE signals for abuse are not generated. For example, dizziness and sedation or sleepiness are common clinical events in elderly patients with Alzheimer's disease.

Since to date no abuse related TEAE attributable to COR388 HCl have occurred, focus will be on a restricted set of index events for which narratives will only be prepared where the causality relationship to COR388 HCl is probable or definite. Information included in the narratives will consist of time to onset/offset, time course of severity, all concurrent events, concurrent medications, and time of onset of events relative to ingestion of COR388 HCl.

The index TEAEs will include:

- Any reports of altered perception or hallucinations
- Dizziness
- Euphoric mood
- Feeling drunk
- Feeling of relaxation
- Sedation
- Somnolence

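### The adverse-event intensity scale grades by effect on functioning alone, so an asymptomatic ALT/AST rise that requires stopping study drug fits only Mild in the severity table

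*Protocol*

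**What the plan says.** Section 9.1.5 defines the scale: "Intensity refers to the severity of an event and references impact on a subject's functioning". One set of three definitions then applies to every adverse event:

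- The lowest grade, Mild, reads "The AE does not interfere in a significant manner with the subject's normal level of functioning". It sets no condition about hazard.
- The middle grade, Moderate, calls for a degree of impairment and rules out any hazard to health.
- The top grade, Severe, brings the two dimensions together: "The AE produces significant impairment of functioning or incapacitation and is a definite hazard to the subject's health".

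The protocol states no separate grading for laboratory events.

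Under Section 9.1.4 a new or worsened laboratory abnormality is recorded as an adverse event if, among other conditions, it "Leads to discontinuation of investigational product". Section 8.24 lists four criteria for stopping treatment, the first being "ALT or AST >8xULN".

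The frequency and severity of TEAEs is the first safety endpoint listed in the synopsis and in Section 4.1.2. Section 11.3.3.1 says that "TEAEs by maximum severity and relationship to study drug will be summarized", with a breakdown by system organ class, preferred term and arm.

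**The concern.** Functional impact is a workable measure for symptoms. It says little about a laboratory abnormality, because a large enzyme rise may leave the patient feeling and functioning as before. Yet the scale covers laboratory events and offers no other basis for grading them.

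Liver events are where this matters most. Liver monitoring was made more frequent on the DMC's recommendation, and Section 8.24 is given over to drug-induced liver injury. If laboratory-only liver events all fall into the Mild row, the arms can look similar for moderate and severe TEAEs even though liver criteria are stopping treatment more often in one arm.

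The definitions also bring in a second dimension, hazard to health, and do so unevenly: Mild is silent on it, Moderate excludes it and Severe mentions it. The same degree of impairment can then receive different grades in an unexpected order.

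**Working it through.** No sample size, alpha or power figure bears on this, so the check is logical.

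**Step 1. Which stopping criteria need no symptom?** From Section 8.24:

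| Criterion for stopping | Can be met on laboratory values alone? |
|---|---|
| ALT or AST above 8 times ULN | Yes |
| ALT or AST above 5 times ULN for over 2 weeks | Yes |
| ALT or AST above 3 times ULN, with bilirubin above 2 times ULN or INR above 1.5 | Yes |
| ALT or AST above 3 times ULN with listed symptoms or signs | Usually no |

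That gives 3 of 4. The count is conservative, because eosinophilia, itself a laboratory finding, is on the list for the fourth criterion.

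**Step 2. Is such a rise an adverse event?** Yes, if it is new or worsened and leads to stopping the drug (Section 9.1.4).

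**Step 3. Which grade fits?** Take an asymptomatic ALT of 10 times ULN. Functioning is unaffected. Moderate fails because it needs some impairment. Severe fails because it needs significant impairment or incapacitation, however its *or* and *and* are grouped. Mild is met. An asymptomatic ALT just above 3 times ULN that was recorded as an adverse event would get the same grade.

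**Step 4. What do the hazard clauses do?** Cross impairment with hazard and apply the wording:

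| Impairment | Not hazardous | Hazardous |
|---|---|---|
| None | Mild | Mild |
| Some, not significant | Moderate (Mild's words are also met) | Mild only |
| Significant | Severe or no grade, depending on how Severe is parsed | Severe |

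In the middle row, adding hazard lowers the grade. Moderate is ruled out by the hazard, Severe by the lack of significant impairment, and only Mild remains. In the bottom left cell, the event is Severe if hazard attaches only to incapacitation. It has no grade if hazard is required in every case.

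**Step 5. Where else do these events appear?** Section 11.3.3.1 also tabulates TEAEs leading to discontinuation and SAEs by treatment group. Section 11.3.3.2 gives means, changes, shift tables, the frequency of abnormalities, and listings that flag marked values. The shift tables are described as normal versus abnormal, so values of 1.1 and 10 times ULN share a cell. No table by arm and multiple of ULN is named.

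**The case against.** The strongest reply is that only one descriptive table is affected. The stopping and rechallenge rules in Section 8.24 rest on laboratory values and symptoms, and Section 9.1.2 ties regulatory reporting to seriousness and not to severity. A reader might infer that the scale hides the liver events. The protocol does not support that. An event that stops treatment is counted by arm in the discontinuation table, can be an SAE as an important medical event, and is visible in the laboratory outputs and to the DMC.

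Three other inferences also fail.

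- *Liver toxicity is the trial's main safety signal.* The protocol shows heightened liver monitoring but ranks no signals, and it gives no reason for the partial clinical hold.
- *Sections 9.1.2 and 9.1.5 flatly contradict each other.* Section 9.1.2 observes that an event called severe may matter little medically, with a headache as the example. This conflicts with 9.1.5 only if Severe always requires hazard. It is also a remark on usage, not a grading rule.
- *Meeting a stopping criterion makes an event hazardous in the sense of 9.1.5.* Section 8.24 does not say so, and the conclusion in Step 3 does not need it.

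It can also be said that a table by multiple of ULN is ordinary SAP content. That is fair as far as the table goes. But the investigator assigns intensity on the eCRF using the protocol's definitions. An SAP can add a derived category, but it cannot change what was asked at collection.

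**Conclusion.** The point holds in limited form. Under the wording of Section 9.1.5, any asymptomatic ALT/AST rise that meets one of the three laboratory-only stopping criteria fits no grade but Mild, so the maximum-severity table understates liver events. This follows from the definition. It is not an estimate, and the protocol gives no event numbers from which the effect on the table could be sized.

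It assumes that investigators apply the definitions literally and that the event has no effect on functioning. If some are swayed by the word hazard and grade higher, the result is inconsistent grading, which also weakens the table.

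The hazard clauses are a second, smaller defect. They lower the grade of one class of events and leave Severe ambiguous. Whether any combination is left wholly without a grade depends on how Severe is read, so no firm count of ungraded cells should be claimed.

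The discontinuation table and laboratory outputs limit the harm but do not remove it, because severity is part of the first-listed safety endpoint and the shift tables described do not separate small from large rises.

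**What to change.** Reconcile Section 9.1.5 with Sections 9.1.2, 9.1.4 and 8.24:

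1. Remove the hazard clauses from Moderate and Severe, so that intensity is one axis (functioning) and hazard is left to seriousness.
2. State that functional intensity does not grade laboratory adverse events. Step 1 alone would still leave asymptomatic liver events at Mild.
3. Beside the severity table, report laboratory-defined liver events by treatment arm in categories of peak ALT/AST at the multiples Section 8.24 already states (above 3, 5 and 8 times ULN), plus the combined category with bilirubin or INR. Derive these from existing laboratory data, fix the derivation before unblinding, and keep the investigator's grade. These are reporting categories. They need not be mapped to Mild, Moderate and Severe, and a peak category does not by itself show how long a rise lasted.

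No stopping or treatment rule changes. The cost is a wording amendment, one derived variable and one table. Two classifications will be held for laboratory events, and the reported picture for liver events will look less favourable.
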